IRB#: 13-244 A(9)

#### 1.0 PROTOCOL SUMMARY AND/OR SCHEMA

This is a single-arm phase II study evaluating the clinical efficacy of regorafenib in the treatment of patients with progressive, recurrent/metastatic adenoid cystic carcinoma (ACC). Any number of prior therapies for recurrent/metastatic ACC is allowed. There are two primary endpoints for the study: 1) proportion of patients alive at 6 months without disease progression by RECIST v1.1 criteria (6-month PFS), and 2) best overall response rate (BOR = CR+PR) documented by RECIST v1.1 criteria. The secondary endpoints are the safety and tolerability of regorafenib. An exploratory endpoint is analyzing tumor tissues for biomarkers that correlate to regorafenib clinical efficacy. Patients enrolled in the study will be treated with regorafenib 160 mg orally daily for 3 weeks in a 4 week cycle. Dose reductions and delays can be implemented according to criteria outlined in Section 11. RECIST v1.1 tumor assessments will be made at baseline (CT or MRI) and then approximately every 2 cycles (or every 8 weeks (+/- 1 week)). After 10 months, imaging will be done approximately every 3 cycles (or every 12 weeks (+/- 1 week)). Patients may remain on study until progression of disease or unacceptable toxicity. Other reasons patients could potentially come off study include patient non-compliance, patient withdrawal of consent, or physician's clinical judgment that removal of the patient from the study is in his/her best interest.

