#### 4.2 Intervention

All eligible patients will receive a starting regorafenib dose of 120 mg daily taken orally for 3 weeks in a 4-week cycle. Patients for whom regorafenib dose reduction was not performed or required may have their treatment dose increased to the FDA-approved dose of 160 mg daily orally for 3 weeks in a 4-week cycle in cycle #2 or beyond (this is not mandatory). RECIST v1.1 tumor assessments will be made at baseline (CT or MRI) and then approximately every 2 cycles (or every 8 weeks (+/- 1 week)). After 10 months, imaging will be done every 3 cycles (or every 12 weeks (+/- 1 week)). Patients may remain on study until progression of disease or unacceptable toxicity

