#### 9.0 TREATMENT/INTERVENTION PLAN

#### 9.1 Administration

Regorafenib 120 mg daily taken orally will be administered for 3 weeks on /1 week off. One cycle is 28 days. Three 40-mg regorafenib tables should be taken in the morning with approximately 8 fluid ounces (240 mL) of water after a low-fat (<30% fat) breakfast. Some examples of low fat breakfasts are:

IRB PB

IRB#: 13-244 A(9)

- Two slices of white toast with 1 tablespoon of low-fat margarine and 1 tablespoon of jelly and 8 ounces (240 mL) of skim milk (approximately 319 calories and 8.2 g of fat).
- One cup of cereal (i.e. Special K), 8 ounces (240 mL) of skim milk, one piece of toast with jam (no butter or marmalade), apple juice, and one cup of coffee or tea (2 g fat, 17 g protein, 93 g of carbohydrate, 520 calories.

Patients for whom regorafenib dose reduction was not performed or required may have their treatment dose increased to the FDA-approved dose of 160 mg daily orally for 3 weeks in a 4-week cycle in cycle #2 or beyond (this is not mandatory).

If doses are missed or vomited, this must be indicated in the patient's pill diary. Missed doses not directed by the investigator(s) that constitute ≤ 20% of the mandated doses for a given cycle will not be considered (a) protocol violation(s). Missed or skipped doses will not be made up (i.e., the week/day count on therapy will continue regardless of whether doses have been missed or skipped). Study treatment will be administered in cycles of 4 weeks in duration. Patients will bring their pill diaries for review at their clinic visits but it will not be considered a protocol violation if the patient forgets the diary.

Patients will receive a sufficient supply of study drug to last until their next scheduled appointment.

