#### 9.3 Schedule of Events (for ALL patients initiating treatment)

- 9.3.1 Patients will initiate treatment with regorafenib on Week 1, Day 1. The required laboratory tests (detailed in **Section 10**) can be performed up to 7 days prior to initiation of treatment. It is unnecessary to repeat these laboratory tests if the screening assessments of the same tests were performed within 7 days prior to first dose of therapy. All other Week 1 evaluations (detailed in **Section 10**) may be performed up to 3 days prior to initiation of study treatment.
- 9.3.2 The onset of regorafenib-induced hypertension often occurs during the first cycle of treatment for most patients who develop hypertension. During the first 6 weeks of treatment, it is strongly recommended that patients have their blood pressures checked even in weeks that they are not evaluated at MSKCC. There are no restrictions on how the blood pressure is to be obtained during those weeks, and can include monitoring on home blood pressure equipment, at other physician offices, at MSKCC, or at commercial outlets. Blood pressure values may be recorded in the pill diaries that will be reviewed at each MSKCC clinic visit or verbally reported to the study team. If the systolic blood pressure is >150 mm Hg and/or the diastolic blood pressure is > 90 mm Hg and/or symptoms develop that are perceived to be related to elevated blood pressure (for example headaches or visual disturbance), patients will be instructed by study staff to contact their study physician immediately for guidance. A re-check of the blood pressure can be requested at the study physician's discretion to determine the accurate value of the patient's blood pressure before protocol-dictated action(s) is/are taken in response to a reported blood pressure value (this applies both to recommended and protocolmandated blood pressures taken at MSKCC or outside of MSKCC). The study

IRB#: 13-244 A(9)

physician may at his/her discretion determine which external values likely reflect the true blood pressure to guide clinical decision-making.

- 9.3.3 Patients for whom regorafenib dose reduction was not performed or required may have their treatment dose increased to the FDA-approved dose of 160 mg daily orally for 3 weeks in a 4-week cycle in cycle #2 or beyond (this is not mandatory).

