	a: See Section 8.0 for the timing of these tests/evaluations prior to the start of therapy. b: Patients will start the study taking regorafenib 120 mg orally daily for 3 weeks in a 4 week cycle. Patients for whom regorafenib dose reduction was not performed or required may have their treatment dose increased to the FDA-approved dose of 160 mg daily orally for 3 weeks in a 4-week cycle in cycle #2 or beyond (this is not mandatory). If a patient misses a dose of regorafenib for personal reasons (i.e. forgetting to take medication, nausea, etc.), the missed dose should be documented on the patient's pill diary (Appendix B). Missed doses not directed by the investigator(s) that constitute ≤ 20% of the mandated doses for a given cycle will not be considered (a) protocol violation(s). Doses held at the discretion of the physician are never protocol violations. Missed or skipped doses will not be made up (i.e., the week/day count on therapy will continue regardless of whether doses												

IRB#: 13-244 A(9)

have been missed or skipped).

- c: Albumin, alkaline phosphatase, total bilirubin, bicarbonate, BUN, calcium, chloride, creatinine, glucose, LDH, phosphorus, potassium, total protein, SGOT [AST], SGPT [ALT], sodium.
- d: These Week 1 evaluations may be performed up to 3 days prior to the start of treatment.
- e: These Week 1 laboratory tests may be done up to 7 days prior to starting treatment. It is unnecessary to repeat these laboratory tests if the screening assessments of the same tests were performed within 7 days prior to the first dose of therapy.
- f: After the completion of Cycle 2, the CBC, serum chemistry blood tests, coagulation studies (if required), physical examinations, vitals signs, performance status, and weight will be done once every cycle, preferably on week 1 of every cycle. If the patient cannot be seen on week 1, these evaluations may be completed up to 1 week prior or during another week within the cycle at the discretion of the treating physician.
- g: Off-study evaluation will be performed within 30 days of the patient's last dose of regorafenib.

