#### 11.0 TOXICITIES/SIDE EFFECTS

The starting dose of regorafenib is 120 mg once daily. Study medication will be administered on a 3 weeks on/1 week off schedule (3 weeks out of every 4). Patients for whom regorafenib dose reduction was not performed or required may have their treatment dose increased to the FDA-approved dose of 160 mg daily orally for 3 weeks in a 4-week cycle in cycle #2 or beyond (this is not mandatory).

Doses will be delayed or reduced for clinically significant hematologic and non-hematologic toxicities that are related to protocol therapy according to the guidelines described in sections below. Dose modifications will follow predefined dose levels. Dose adjustments for hematologic toxicity are based on the blood counts obtained in preparation for the day of treatment.\

For patients who must undergo a procedure or surgery while on study that requires wound healing or involves risk for significant bleeding, regorafenib should be held 2 weeks prior to the scheduled surgery/procedure. The decision to resume reografenib after the surgery/procedure should be based on clinical judgement of adequate wound healing

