#### 11.1 General Considerations for Managing Regorafenib-related Adverse Events

This section contains general recommendations for the management of adverse events. Patients developing a regorafenib-related CTCAE Grade 1 or 2 adverse events may have their dose continued at the same dose level.

Notes: The recommendations for the management of adverse events in this section are to serve as general guidelines; dose reductions or delays for any event of any CTCAE grade may always be considered for safety reasons at the discretion of the treating investigator. If a subject experiences more than one toxicity, dose reduction should be according to the toxicity with the highest grade. In the case of two or more toxicities of the same grade, the investigator may dose reduce according to that deemed most causally related to study treatment.

The modifications of regorafenib will follow the following predefined dose levels:						
Dose level +1 (standard starting dose) 160 mg po qd Four 40-mg tablets of regorafenib						
Dose level 0	120 mg po qd Three 40-mg tablets of regorafenib					
Dose level - 1	80 mg po qd	Two 40-mg tablets of regorafenib				

(RB PB

IRB#: 13-244 A(9)

	Recommended dose modification for toxicities except hand-foot-skin reaction, hypertension, and ALT/AST/bilirubin for adverse events related to regorafenib						
NCI-CTCAE v4.0 a	Dose Interruption b	Dose Modification b	Dose for Subsequent Cycles				
Grade 0-2	Treat on time	No change	No change				
Grade 3	Delay until ≤ Grade 2°	Reduce by 1 dose level	If dose was reduced and toxicity remains < Grade 2, dose re-escalation can be considered at the discretion of the treating investigator. If dose is re-escalated and toxicity (≥ Grade 3) recurs, institute permanent dose reduction.				
Grade 4	Delay until ≤ Grade 2°	Reduce by 1 dose level. Permanent discontinuation can be considered at treating investigator's discretion.					

a. NCI-CTCAE = National Cancer Institute - Common Terminology Criteria for Adverse Events, version 4.0

(RB PB

b. Dose modification or interruption is not required for alopecia, non-refractory hypersensitivity and asymptomatic laboratory abnormalities. Dose modification or interruption is not required for nausea, vomiting and diarrhea if optimal supportive management has not been instituted.

c. If no recovery after a 4 week delay, treatment should be permanently discontinued unless subject is deriving clinical benefit.

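### Section 1.0 gives 160 mg daily without qualification, while Sections 4.2, 9.1, 10.0 and 11.0 start every patient at 120 mg; the two accounts of cycle 1 must be reconciled

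*Combined protocol and SAP*

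**What the plan says.** The protocol summary (Section 1.0) gives one dose for the trial: "Patients enrolled in the study will be treated with regorafenib 160 mg orally daily for 3 weeks in a 4 week cycle". It adds that reductions and delays follow Section 11. It mentions neither a lower starting dose nor an escalation step.

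Four other places give a different start:

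- Section 4.2: "All eligible patients will receive a starting regorafenib dose of 120 mg daily taken orally for 3 weeks in a 4-week cycle".
- Section 9.1 also gives 120 mg, and backs it with a tablet count: "Three 40-mg regorafenib tables should be taken in the morning".
- Section 10.0, study calendar, footnote b: "Patients will start the study taking regorafenib 120 mg orally daily for 3 weeks in a 4 week cycle".
- Section 11.0: "The starting dose of regorafenib is 120 mg once daily".

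Each of these four, and Section 9.3.3, says that patients who have not needed a reduction "may have their treatment dose increased to the FDA-approved dose of 160 mg daily orally for 3 weeks in a 4-week cycle". Each places the increase no earlier than the second cycle and says that it is optional.

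The dose-level table in Section 11.1 has three rungs. The top one reads "Dose level +1 (standard starting dose) 160 mg po qd Four 40-mg tablets of regorafenib". Level 0 is "120 mg po qd Three 40-mg tablets of regorafenib". Level -1 is 80 mg, two tablets, and nothing is listed below it.

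**The concern.** The cycle-1 dose is a safety instruction and should have one reading. Under Section 1.0 a patient takes 160 mg from the first day. Under the other sections 160 mg is available only later, only to patients who have not needed a reduction, and only as an option. So the summary gives unconditionally, at the outset, a dose that the rest of the protocol makes conditional on tolerability. Safety and tolerability are the secondary objective, and Section 4.1 frames the conclusion as whether the regimen deserves further study, so the protocol should describe that regimen in one way.

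The practical risk lies with someone who works from the summary alone. All of the text is current; Section 1.0 is not an amendment log.

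A smaller and separate matter is the bottom of the dose-level table. Section 11.0 ties dose modifications to predefined levels, but several toxicity rules can call for one level down when the patient is already on the lowest level listed.

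**Working it through.** **1. Cycle-1 dose, side by side**

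| Place | Dose at start | 160 mg |
|---|---|---|
| 1.0 | 160 mg | stated for all enrolled patients, no condition |
| 4.2 | 120 mg | optional, cycle 2 or later, no prior reduction |
| 9.1 | 120 mg (three tablets) | same |
| 10.0, footnote b | 120 mg | same |
| 11.0 | 120 mg | same |
| 9.3.3 | not stated | same |

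Inputs: 40-mg tablets (Sections 9.1 and 11.1); 3 weeks of dosing per 28-day cycle, so 3 × 7 = 21 dosing days.

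- Tablets per day: 160/40 = 4; 120/40 = 3.
- Tablets in cycle 1: 4 × 21 = 84; 3 × 21 = 63.
- Milligrams in cycle 1: 160 × 21 = 3,360; 120 × 21 = 2,520.
- Ratio: 160/120 = 1.33.

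These figures restate the gap between the two texts. They do not measure what any patient received.

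**2. Effect on the decision rules**

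Section 14.0 sets at least 5 responses in 38 patients (5% against 20%) and at least 21 of 38 progression-free at 6 months (40% against 65%). Exact binomial tails give:

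- Response: type I error 0.0397, power 0.901.
- 6-month PFS: type I error 0.0409, power 0.921.
- Either endpoint, under independence: 1 − (1 − 0.0397)(1 − 0.0409) = 0.079, consistent with the stated bound of 0.1.

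Dose is not an input to any of these.

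**3. The bottom of the dose-level table**

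Listed levels are 160, 120 and 80 mg. Levels remaining below each: two, one and none. Rules that can ask for one level down in a patient already at 80 mg:

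| Rule | When | Exit by number of reductions |
|---|---|---|
| 11.1 general table | Grade 3 or Grade 4 event | none stated |
| 11.2 hand-foot skin reaction | for example Grade 3, first or second occurrence; Grade 2, third occurrence | more than 2 |
| 11.3 hypertension | Grade 3 not controlled, or recurring after a reduction | more than 2 |
| 11.4 liver tests | first qualifying rise, if 80 mg was reached for another toxicity | none stated (re-occurrence leads to discontinuation) |

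Three paths, counting reductions cumulatively (the text does not say how to count across toxicities):

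- 120 → 80 → next trigger: this is the second reduction, so the more-than-2 exit is not met, and no level is listed.
- 160 → 120 → 80 → hand-foot or hypertension trigger: this is the third reduction, so the exit applies.
- 160 → 120 → 80 → another Grade 3 event under the general table: no level is listed and that table has no count-based exit.

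The gap is therefore not confined to patients who stayed at or below the 120 mg start.

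**The case against.** The strongest reply is that this is one sentence in a summary. The sections a prescriber would use agree with each other, Section 9.1 gives the tablet count as well as the milligrams, and Section 1.0 sends the reader for dose changes to Section 11, which opens with the 120 mg start. All of that stands, and it limits the practical risk. It does not remove the contradiction: a summary may leave out detail, but this one states a different dose.

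A reader might take the Section 11.1 label on the 160 mg level as a second contradiction. The documents do not go that far. The label may refer to the approved dose outside this trial, which the protocol itself puts at 160 mg, and numbering 120 mg as level 0 fits a 120 mg start. The label is ambiguous.

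On the 80 mg point, Section 11.1 calls its recommendations general guidelines and leaves reductions and delays to the investigator. Its general table also lets the investigator consider stopping after a Grade 4 event, and Sections 9.3.7 and 13.0 allow treatment to end for unacceptable toxicity or on the investigator's judgment. An investigator is therefore never without a course of action. What remains is that no sentence says what applies when a reduction is called for at 80 mg.

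**Conclusion.** The contradiction holds: the plan is wrong as written, because it carries two cycle-1 doses that differ by one 40-mg tablet a day (33%). This rests only on reading Section 1.0 as it stands, with no qualification as to cycle. Correction is needed because the item is a dosing instruction; the number of sections affected is not the reason.

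Two stronger inferences are not supported. A reader might infer that patients were started at different doses; nothing in the documents shows this. A reader might also infer that the efficacy conclusions are compromised; the sample size, thresholds and error rates in Section 14.0 are unchanged.

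The 80 mg gap is a minor clarification and does not share the weight of the main point. The documents give no figure for how many patients would be at that level.

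**What to change.** Reconcile Section 1.0, and the label on the 160 mg level in Section 11.1, with Sections 4.2, 9.1, 9.3.3, 10.0 (footnote b) and 11.0, so that one starting dose and one escalation rule appear throughout. The sponsor decides which text is intended.

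Separately, reconcile the Section 11.1 dose-level table with the reduction wording in Sections 11.1 to 11.4, so that the text states what applies to a patient at 80 mg who meets a further reduction trigger. No dose or reduction rule is proposed here.

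The cost is a wording amendment. It needs no extra patients or procedures and no change to the statistical decision rules.

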#### 2.0 OBJECTIVES AND SCIENTIFIC AIMS

#### **Primary Objectives**

- 1) To determine the proportion of patients alive at 6 months without disease progression by RECIST v1.1 criteria of patients with progressive, recurrent/metastatic ACC treated with regorafenib.
- 2)To determine the best overall response rate documented by RECIST v1.1 criteria of patients with progressive, recurrent/metastatic ACC treated with regorafenib.

#### **Secondary Objective**

To determine the safety/tolerability of regorafenib.

#### **Exploratory Objective**

To perform tumor tissues analyses for putative biomarkers and explore their association with regorafenib clinical efficacy.

#### 3.0 BACKGROUND AND RATIONALE

#### Recurrent/metastatic (R/M) ACC

Adenoid cystic carcinomas (ACCs) are malignant neoplasms composed of epithelial and myoepithelial cells that commonly arise from both minor and major salivary glands. Rarely, ACC may also originate at other sites, such as the trachea, lung, and breast. While localized disease is potentially curable, nearly 40% of patients develop distant metastasis despite aggressive surgery and radiation with disease-free intervals ranging from 1 month to 19 years. Metastatic disease is incurable and can be either indolent (10% of patients with distant metastases survive more than 10 years) or alternatively more aggressive (54% of patients with distant metastases survive less than 3 years). There are no effective therapies and the development of new treatments is urgently needed.

IRB PB

IRB#: 13-244 A(9)

#### Systemic therapies tested in R/M ACC to date possess limited effectiveness

We conducted an exhaustive review of all chemotherapy studies conducted between 1966 and 2009 for R/M ACC which included 34 clinical trials that involved less than 500 patients. Most were small, single institution studies of variable methodological quality. In this literature, only 18 objective major responses out of 141 patients (13%) treated with single agent cytotoxic chemotherapy were reported. Mitoxantrone as a single agent was studied in the most number of patients in clinical trials of variable quality; the pooled response rate (an imperfect estimate of true activity) from these studies was around 10%. Ultimately, the true response rate of cytotoxic chemotherapy can only be concluded to be modest; the actual rate of response is difficult to ascertain across several different trials of variable quality. Insufficient data exists to suggest that combination chemotherapy improves response rates or clinical benefit over single agent treatment.

Given the limited efficacy of cytotoxic drugs, several targeted therapies have also been tested. With up to 90% of ACC tumors possessing high c-kit expression and case reports of responses to imatinib, six studies have been reported for imatinib in ACC with disappointingly only 2 objective responses in 71 evaluable patients. Studies with gefitinib, cetuximab, lapatinib, and bortezomib all have failed to yield any objective responses.

[figure not shown]
#### The oncogenic transcription factor c-myb is overexpressed in ACC

In 2009, Persson et. al. confirmed the existence of a t(6;9)(q22-23;p23-24) translocation in ACC tumors of the breast and head/neck (Figure 1A). This cytogenetic alteration creates a gene fusion of the c-myb and NFIB transcription factors. The translocation was identified in all 11 tumors analyzed. The *MYB-NFIB* fusion characterized in that publication predominantly involved a breakpoint between intron 14 of *MYB* and intron 8 of *NFIB*. Minimally, this resulted in the loss of the last 38 amino acids on the c-myb protein and the addition of the last 5 amino acids of the NFIB protein to the C-terminal end of the truncated c-myb gene (Figure 1). This results in the loss of several microRNA binding sites in the 3' UTR ("untranslated region") of the *MYB* gene, leading to upregulated levels of c-myb expression in ACC tumors relative to non-ACC tumors at both the mRNA transcript and protein level. c-myb overexpression presumably enhances transcriptional activity of c-myb, leading to the overexpression of 14 *MYB* target genes, including *vascular endothelial factor A (VEGFA), KIT, fibroblast growth factor -2 (FGF2),* and *BCL2*, all of which have been previously proposed to be potentially critical genes for therapeutic targeting in ACC.

IRB#: 13-244 A(9)

**Figure 1**. Schematic of the t(6;9) translocation. *DBD*, DNA Binding Domain; *TAD*, Transactivation Domain; *NRD*, Negative Regulatory Domain; *miR*, microRNA. Adapted from Persson et. al. "Recurrent fusion of MYB and NFIB transcription factor genes in carcinomas of the breast and head and neck". PNAS, 2008.

Mitani et. al. recently published a comparative analysis of 123 salivary gland cancers (72 primary ACC tumors, 17 ACCs metastatic to the lung and lymph nodes, and 34 salivary tumors of other non-ACC histologies) and 5 normal salivary gland tissue samples. These authors observed that the *MYB-NFIB* fusion gene was present in 27.7% of primary ACCs, 35.2% of metastatic ACCs, and none of the non-ACC salivary cancer histologies or normal salivary tissues. As expected, elevated *MYB* expression was detected in 85% of fusion positive tumors at about 100-fold higher levels than non-ACC tumors. Interestingly, 70% of fusion negative tumors also demonstrated elevated c-myb expression at an approximately 40-fold higher level over non-ACC tumors and just 2-fold lower than fusion-positive ACCs, suggesting alternate mechanisms of c-myb overexpression and supporting the hypothesis that c-myb plays a central role in the pathogenesis of this disease.

c-myb is a bona fide oncogene. It was first discovered as the transforming gene co-opted by the Avian myeloblastosis virus (AMV) and later the *MYB* gene locus was identified as a common integration site for several avian and murine retroviruses leading to the development of leukemia. It was recently reported that the *MYB* gene locus is involved with chromosomal translocations and genomic duplications associated with a new subtype of human T-cell acute leukemia. *MYB* overexpression has also been described in solid tumors. In colon cancer, *MYB* overexpression has been reported in >80% of cases and when found expressed with Bcl-xl correlates with poor prognosis. *MYB* overexpression has also been implicated in the pathogenesis of breast, melanoma, pancreatic, and esophageal cancers.

Results from two whole exome and genome sequencing projects in ACC have recently been reported . These analyses revealed a relatively "quiet" genome with a low somatic mutation rate (0.31 non-silent events per megabase ) and wide mutational diversity. These studies verified the importance of MYB in ACC biology with one study confirming 57% of tumors possessed the *MYB-NFIB* translocation and an additional 8% had alterations resulting in MYB pathway dysregulation . Mutations in chromatin-remodeling genes were also a prominent feature in the genetic landscape of ACCs (35%  and 50%  rates of mutation in the two studies). Alterations in several other biologic pathways were found to occur at lower frequencies.

Targeting c-myb activity in ACC

IRB#: 13-244 A(9)

Devising strategies to directly block the function of a non-kinase transcription factor is a challenge. One approach is to inhibit the activity of critical c-myb target genes responsible for promoting oncogenesis. An analysis of 7 fusion positive ACC tumors confirmed that *MYB* overexpression indeed correlates to upregulation of 14 *MYB* transcriptional target genes, including the regorafenib-relevant targets *VEGFA* (ligand that induces angiogenesis by engaging VEGF receptors (VEGFRs)), FGF2 (ligand that activates a subset of FGF receptors (FGFRs)), and the receptor tyrosine kinase (RTK) *KIT* (c-kit).

